10.1.2 BMS-986226 and Nivolumab or Ipilimumab Combination Therapy Cohorts (Parts B and C)

The purpose of the combination cohort phase of the study is to gather safety, tolerability, preliminary efficacy, PK, and PD information regarding BMS-986226 in combination with either nivolumab (Parts B) or ipilimumab (Parts C). For each dose level of the Parts B1 and C1, approximately 6 evaluable participants will be treated. This sample size also provides each dose level in Parts B1 and C1 with about 80% probability to detect any AE with an event rate of 24%. Approximately 6-12 evaluable participants may be treated at each dose level for Parts B2 (BMS-986226 + nivolumab) and C2 (BMS-986226 + ipilimumab) if additional safety, PD, or PD data is required to optimize dose and/or schedule selection. With up to 12 evaluable participant in each of Parts B2 and C2, it provides each dose level with up to 96% probability to detect any AE with an event rate of 24%.

Once the safety (during the DLT evaluation) of a combination of BMS-986226 and nivolumab (ipilimumab) has been established and a recommended BMS-986226 dose regimen has been selected for Part D (E), additional participants (up to 6 additional evaluable participants for each of nivolumab and ipilimumab in combination with BMS-986226) may be treated at the recommended dose to better characterize the safety, PK, and PD profile.

During this part of the study, the BLRM-Copula model, incorporating single-agent toxicity profiles of both BMS-986226 (Part A) and nivolumab or ipilimumab, as well as any available information from the combination cohorts, will be used to guide any potential dose recommendation. Details regarding the BLRM-Copula model are given in Appendix 10.

10.1.3 Combination Expansion Arms (Parts D and E)

Approximately 40 evaluable participants will be treated in each of Parts D and E. This sample size provides each cohort with about 87% probability to detect any AE with an event rate of 5%.

10.2 Populations for Analyses

Population	Description
Enrolled	All participants who have signed an ICF and are registered into the IRT
Treated	All participants who received any dose of study treatment
Response-evaluable	All treated participants with measurable disease at baseline and 1 of the following: (1) at least 1 postbaseline tumor assessment, (2) clinical progression, or (3) death.
Pharmacokinetic	All treated participants who have evaluable concentration-time data.

For purposes of analysis, the following populations are defined:

Population	Description
Immunogenicity	All treated participants who have a baseline and at least 1 postbaseline immunogenicity measurement.

Abbreviations: ICF = informed consent form; IRT = Interactive Response Technology.

Analyses of safety, extent of exposure, **PK**, efficacy, and immunogenicity will be based on all treated participants.

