Eligible participants will have advanced solid tumors, including, but not limited to cervical cancer (CC), colorectal cancer (CRC), head and neck squamous cell carcinoma (HNSCC), melanoma (MEL), non-small cell lung cancer (NSCLC), prostate cancer (PRC), renal cell carcinoma (RCC), triple negative breast cancer (TNBC) and urothelial carcinoma (UCC). There must be histological or cytological confirmation of a malignancy that is advanced (metastatic and/or unresectable) with measureable disease as defined by Response Evaluation Criteria In Solid Tumors (RECIST) v1.1 or Prostate Cancer Working Group 3 (PCWG 3) (prostate only), including at least 1 lesion accessible for biopsy in addition to the target lesion.

Objectives and Endpoints:

Objective	Endpoint
Primary	
To characterize the safety and tolerability of BMS-986226 administered alone and in combination with nivolumab or ipilimumab in participants with advanced solid tumors	Incidence of AEs, SAEs, AEs meeting protocol defined DLT criteria, AEs leading to discontinuation, and AEs resulting in death. Incidence of clinical laboratory test abnormalities
Secondary	
To explore the preliminary efficacy of BMS-986226 administered alone and in combination with either nivolumab or ipilimumab in participants with advanced solid tumors	ORR, median DOR, and PFS rate at 24 weeks ^a
To characterize the PK of BMS-986226 when administered alone and in combination with either nivolumab or ipilimumab in participants with advanced solid tumors	PK parameter estimates of BMS-986226
To characterize the immunogenicity of BMS-986226 when administered alone and in combination with either nivolumab or ipilimumab in participants with advanced solid tumors	Incidence of anti-drug antibodies (ADA) specific for BMS-986226
To monitor target engagement of BMS- 986226 administered alone and in combination with either nivolumab or ipilimumab in participants with advanced solid tumors	Summary measures of changes from baseline (% or absolute change) in cell surface ICOS expression on T cells and ICOS-ligand + B cells

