7 TREATMENT

Study treatment is defined as any investigational treatment(s) or marketed product(s) intended to be administered to a study participant according to the study randomization or treatment allocation.

Study treatment includes IPs/investigational medicinal products (IMPs) and non-IPs/IMPs and can consist of the following:

- BMS-986226
- Nivolumab
- Ipilimumab
- Tetanus Vaccine

An IP, also known as IMP in some regions, is defined as a pharmaceutical form of an active substance or placebo being tested or used as a reference in a clinical study, including products already with a marketing authorization but used or assembled (formulated or packaged) differently from the authorized form, used for an unauthorized indication, or when used to gain further information about the authorized form.

Other medications used as support or escape medication for preventative, diagnostic, or therapeutic reasons, as components of the standard of care for a given diagnosis, may be considered as non-IPs.

Product Description / Dosage Form	Potency	IP/NonIMP	Blinded or Open Label	Packaging / Appearance	Storage Conditions (per Label)
BMS-986226-01 Solution for Injection	10 mg/mL	IP	Open	Vial	2 to 8 °C, Protect from light
Nivolumab Solution for Injection	10 mg/mL	IP	Open	Vial	2 to 8 °C, Protect from light and freezing
Ipilimumab Solution for Injection	5 mg/mL	IP	Open	Vial	2 to 8 °C, Protect from light and freezing
Tetanus vaccine	Per local ^a	IP	Open	Various packaging configuration	Refer to the label on container and/or pharmacy manual

Abbreviations: IP = investigational product

^a Tetanus vaccine (Tdap preferred, Td or equivalent after discussion with the Medical Monitor/Study Director or designee) will be obtained as local commercial product in countries if allowed by local regulations or through investigating sites standard prescribing procedures.

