10.3.4 Immunogenicity Analyses

Endpoint	Statistical Analysis Methods
Incidence of ADA to BMS-986226 Baseline ADA-positive participant is defined as a participant who has an ADA-detected sample at baseline ^a . ADA-positive participant is a participant with at least 1 ADA-positive sample relative to baseline after initiation of the treatment	Frequency distribution of baseline ADA-positive participants and ADA-positive participants after initiation of the treatment

^a Baseline sample is the last sample before initiation of the treatment. Abbreviations: ADA = anti-drug antibody.

Revised Protocol No.: 04 Date: 31-May-2019

11 **REFERENCES**

- ¹ Scott AM, Allison JP, Wolchok JD. Monoclonal antibodies in cancer therapy. Cancer Immun 2012;12:14. Epub 2012 May.
- ² Scott AM, Wolchok JD, Old LJ. Antibody therapy of cancer. Nat Rev Cancer 2012;12(4):278-87. doi:10.1038/nrc3236.
- ³ Gao J, Bernatchez C, Sharma P, et al. Advances in the development of cancer immunotherapies. Trends Immunol 2013;34(2):90-8. doi: 10.1016/j.it.2012.08.004. Epub 2012 Sep 30.
- ⁴ Topalian SL, Weiner GJ, Pardoll DM. Cancer Immunotherapy Comes of Age. J Clin Oncol 2011;29(36): 4828–36.
- ⁵ Postow MA, Callahan MK, Wolchok JD. Immune Checkpoint Blockade in Cancer Therapy. J Clin Oncol 2015;33(17):1974-82. Epub 2015 Jan 20.
- ⁶ Hodi FS, O'Day SJ, McDermott DF, et al. Improved survival with ipilimumab in patients with metastatic melanoma. N Engl J Med 2010;363:711-23. [published erratum appears in, N Engl J Med 2010;363:1290.]
- ⁷ Robert C, Thomas L, Bondarenko I, et al. Ipilimumab plus dacarbazine for previously untreated metastatic melanoma. N Engl J Med 2011;364:2517-26.
- ⁸ Topalian SL, Hodi FS, Brahmer JR, et al. Safety, activity, and immune correlates of anti-PD-1 antibody in cancer. N Engl J Med 2012;366(26):2443-54. doi: 10.1056/NEJMoa1200690. Epub 2012 Jun 2.
- ⁹ Schaer DA, Hirschhorn-Cymerman D, Wolchok JD. Targeting tumor-necrosis factor receptor pathways for tumor immunotherapy. J Immunother Cancer 2014;2:7. doi: 10.1186/2051-1426-2-7. eCollection 2014.
- ¹⁰ Carthon B, Wolchok JD, Yuan J, et al. Pre-operative CTLA-4 blockade: tolerability and immune monitoring in the setting of a pre-surgical clinical trial. Clin Cancer Res 2010;16(10):2861-2871. doi:10.1158/1078-0432.CCR-10-0569.
- ¹¹ Choueiri, TK, Fishman MN, Escudier B, et al. Immunomodulatory Activity of Nivolumab in Metastatic Renal Cell Carcinoma. Clin Cancer Res 2016;22(22):5461-71.

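### Section 10.2 defines an Immunogenicity population but bases the immunogenicity analyses on all treated participants; read as written, ADA incidence can only be understated, by an amount the documents do not fix

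*Combined protocol and SAP*

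**What the plan says.** Section 10.2 introduces its table with "For purposes of analysis, the following populations are defined". Three entries matter here.

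- **Treated:** "All participants who received any dose of study treatment".
- **Immunogenicity:** "All treated participants who have a baseline and at least 1 postbaseline immunogenicity measurement".
- **Closing sentence, after the table:** analyses of several kinds, ending with "efficacy, and immunogenicity will be based on all treated participants".

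Section 10.3.4 sets the numerator: "ADA-positive participant is a participant with at least 1 ADA-positive sample relative to baseline after initiation of the treatment". The planned summary is "Frequency distribution of baseline ADA-positive participants and ADA-positive participants after initiation of the treatment". It names no denominator. No other current section assigns the Immunogenicity population to an analysis.

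The endpoint is listed among the secondary endpoints in the Synopsis as "Incidence of anti-drug antibodies (ADA) specific for BMS-986226".

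Section 7 introduces the products that count as study treatment with "Study treatment includes IPs/investigational medicinal products (IMPs) and non-IPs/IMPs and can consist of the following". The list is BMS-986226, nivolumab, ipilimumab and tetanus vaccine.

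**The concern.** The same section gives two different sets for one analysis. The narrower set has a clear purpose: it keeps only participants whose ADA status can be judged. The closing sentence overrides it with a wider set, and Section 10.3.4 does not say which one governs.

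The choice affects the estimate. ADA positivity needs a post-treatment sample compared with baseline. Someone without those samples cannot enter the numerator, so leaving them in the denominator treats unknown status as negative.

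The protocol has its own reason to want this rate reported cleanly. Section 3.2.2.4 says that preliminary data suggest ADA are forming, that their relation to infusion reactions is not yet known, and that combination treatment might raise ADA formation compared with monotherapy.

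**Working it through.** **Plan's own figure.** There is none to reproduce. The documents state no expected ADA rate, no missing-sample rate and no sample-size basis for immunogenicity.

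**Step 1: the identity.** Let N be the treated participants in a cohort, E those in the Immunogenicity population, x the ADA-positive participants, and f = 1 − E/N. By the definition in 10.3.4 every positive participant lies within E, so

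x/N = (x/E) × (E/N) = (x/E) × (1 − f).

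The all-treated figure is therefore equal to or lower than the figure on the defined population. The relative understatement is exactly f.

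**Step 2: small cohort.** Section 10.1.2 plans about 6 evaluable participants per dose level in Parts B1 and C1. Assume 1 of 6 treated is unevaluable for ADA and 2 are positive. Intervals are Clopper-Pearson 95%.

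- Immunogenicity population: 2/5 = 40.0% (5.3% to 85.3%).
- All treated: 2/6 = 33.3% (4.3% to 77.7%).
- Relative understatement: 1/6, about 17%.

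**Step 3: expansion part.** Section 10.1.3 plans about 40 in each of Parts D and E. Assume 14 positive.

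- All treated: 14/40 = 35.0%.
- With 4 unevaluable: 14/36 = 38.9%.
- With 8 unevaluable: 14/32 = 43.8%.

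**Step 4: range of f.** For an assumed evaluable incidence of 40%:

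| Assumed f | All-treated incidence |
|---|---|
| 0% | 40% |
| 5% | 38% |
| 10% | 36% |
| 20% | 32% |
| 30% | 28% |

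The counts, the 40% and the values of f are all illustrations, not figures from the documents.

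**Step 5: who would be unevaluable.** Tables 9.5-1 to 9.5-4 give the ADA schedule.

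- Preliminary Safety Cohorts and Part A: first scheduled postbaseline sample at Cycle 1 Day 15.
- Parts B1/C1, B2/C2 and D/E: first scheduled on-treatment postbaseline sample at Cycle 2 Day 1.
- All parts: further samples at end of treatment and at the 30-, 60- and 100-day follow-up visits.

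Section 5.1.3.1 requires all three follow-up visits even after new anticancer treatment starts, unless consent is withdrawn. A participant who stops before Cycle 2 is therefore still due ADA samples. Those left without one are mainly early deaths, consent withdrawals, losses to follow-up and participants with missed samples, including a missing baseline.

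**Step 6: who counts as treated.** Treated requires a dose of any study treatment, and Section 7 includes the tetanus vaccine, which is scheduled 3 to 7 days before Cycle 1 Day 1. Taken literally, someone never given BMS-986226 could sit in the denominator for antibodies against it.

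**The case against.** **All treated may name only the source set.** The Immunogenicity definition itself starts from treated participants, so the closing sentence could mean the pool from which evaluable participants are drawn, and nothing states that missing status counts as negative. That reading is possible, and it is why the conclusion is tied to the text as written. But the text does not say so, and the definition is left without any assigned use.

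**The detail is deferred to a SAP.** Section 10.3 says a SAP will be finalized before database lock. It may well settle the denominator. The material available here does not, and a later SAP that used the defined population would depart from the protocol sentence.

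**The effect is small against the imprecision.** This stands. In the cohort of six both intervals span more than 70 percentage points. The endpoint is descriptive, the study tests no formal hypotheses, and no dose or stopping rule in Section 10 or Appendix 10 uses ADA incidence.

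**Stronger readings the documents do not support.**

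- A reader might infer from the Cycle 2 Day 1 sampling that every dropout before Day 29 is lost. The end-of-treatment and follow-up samples contradict that, although Table 2-2 lets the end-of-treatment visit coincide with the most recent on-treatment visit, so it is not always a new sample. Section 9.5 also allows PK serum to be used for immunogenicity if required.
- A reader might infer a known loss of 10% to 20% of the rate. No missing-sample share appears anywhere.
- A reader might infer the same bias for PK, since the sentence also sets the Pharmacokinetic population aside. Section 10.3.3 summarizes parameters mainly by geometric means and coefficients of variation. A participant without concentrations contributes no value, so no dilution is shown.

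**Conclusion.** The conflict is real and lies within one section: a population is defined for the ADA analysis, and a broader one is then assigned. If the closing sentence is followed literally, ADA incidence is multiplied by (1 − f) and can only be understated or unchanged.

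The direction follows from the protocol's definitions. The size does not, because f is not given: it is nil with complete sampling and, as an illustration, 40% against 33% for one unevaluable participant in six. The conclusion assumes that participants of unknown status are kept in the denominator, as the sentence says. It is worth correcting because the endpoint is secondary and the change is nearly free, but it does not threaten the trial's dose decisions or its primary safety objective.

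**What to change.** - **Section 10.2:** amend the closing sentence so that ADA incidence uses the Immunogenicity population, restricted to participants who received BMS-986226. Keep all treated participants for safety, exposure and efficacy.
- **Section 10.3.4:** state the same denominator beside the planned frequency distribution.
- **Reporting:** give, by cohort, the number treated but not ADA-evaluable, so that readers can see f.
- **Consistency edit only:** name the Pharmacokinetic population for PK summaries. No bias is claimed there.

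The cost is one amended sentence, one added sentence and one extra row in the ADA table. Sampling, data collection and sample size do not change.

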10.3 Statistical Analyses

The statistical analysis plan will be developed and finalized before database lock. Below is a summary of planned statistical analyses of the primary and secondary endpoints. In general, summaries will be performed by cohort. If sufficient data are not available such that adequate interpretation of the result is not warranted, some summaries may not be performed and only listings will be presented. Efficacy analyses will be performed using the RECIST v1.1 (all indications except prostate) or PCWG3 criteria (prostate). Details on censoring scheme on time-to-event endpoints such as DOR, PFS, and OS will be described in the SAP. A description of the participant population will be included in the statistical output reported, including subgroup of age, gender, and race.

Endpoint	Statistical Analysis Methods
ORR is defined as the proportion of all treated participants whose BOR is either CR or PR.	Estimate of ORR and corresponding 2-sided exact 95% CI using the Clopper-Pearson method
BOR for a participant will be assessed per RECIST v1.1 or PCWG3 (for prostate cancer) by investigator	
mDOR DOR for a participant with a BOR of CR or PR is defined as the time between the date of first response and the date of the first objectively documented tumor progression per RECIST v1.1 / PCWG3 or death, whichever occurs first.	mDOR using the Kaplan-Meier method and corresponding two 2-sided 95% CI using Brookmeyer and Crowley methodology (using log-log transformation), if appropriate
PFSR at 24 weeks PFS for a participant is defined as the time from the first dosing date to the date of first objectively documented disease progression or death due to any cause, whichever occurs first.	Estimate by the Kaplan-Meier method and corresponding 95% CI will be derived based on Greenwood formula

10.3.1 Efficacy Analyses

Abbreviations: BOR = best overall response; CI = confidence interval; CR = complete response; DOR = duration of response; mDOR = median duration of response; ORR = objective response rate; PCWG = Prostate Cancer Working Group; PFS = progression free survival; PFSR = progression free survival rate; PR = partial response; RECIST = Response Evaluation Criteria In Solid Tumors.

Revised Protocol No.: 04 Date: 31-May-2019

10.3.2 Safety Analyses

All safety analyses for will be performed on the treated population.

Endpoint	Statistical Analysis Methods
Incidence of AEs, SAEs, AEs meeting protocol-defined DLT criteria, AEs leading to discontinuation, deaths AEs will be graded according to CTCAE v4.03 ²⁷ .	DLT rate by dose level; frequency distribution of treated participants with AE using the worst CTC grade. Participants will only be counted (1) once at the preferred term (PT) level, (2) once at the system organ class (SOC) level, and (3) once in the 'Total participant' row at their worst CTC grade, regardless of SOC or PT.
Laboratory abnormalities Laboratory values will be graded according to CTCAE v4.03 ²⁷ .	Laboratory shift table using the worst CTC grade on treatment per participant

Abbreviations: AE = adverse event; CTC = common terminology criteria; CTCAE = common terminology criteria for adverse events; DLT = dose-limiting toxicity; PT = preferred term; SAE = serious adverse event; SOC = system organ class.

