7.1.1 Method of Treatment Assignment

This is an open-label study. All participants must be assigned a participant number upon providing signed written informed consent. Based on the rate of participant enrollment, the Sponsor will implement an IRT to assign participant numbers, study treatment group, and dose level, as well as manage drug supply. During the screening visit, the investigative site will register the participant by an IRT designated by BMS for assignment of a 5-digit participant number that will be unique across all sites. Enrolled participants, including those not dosed, will be assigned sequential participant numbers.

The participant identification number (PID) will ultimately be composed of the site number and participant number. For example, the first participant screened (e.g., enrolled) at site number 1, will have a PID **Example**. Specific instructions for using the IRT will be provided to the investigational sites in a separate instruction manual.

Once it is determined that the participant meets the eligibility criteria following the screening visit, the assigned treatment group and dose level will be provided to the site study team through the IRT prior to the first study treatment administration. The participant will be informed of one of the following:

- Assigned to a part (Preliminary Safety Cohorts and Part A) and dose cohort in the dose escalation portion of the study.
- Assigned to a part (Part B1, B2, C1, or C2) in the combination portion of the study.
- Assigned to the expansion portion of the study (Parts D and E)

During dose escalation, all participants will be assigned to the Preliminary Safety Cohorts, then Part A until the decision is made to start the combination with either nivolumab or ipilimumab. If there are no openings available in the part to which the participant would be assigned by this algorithm, then the participant will be assigned to the next open part/cohort. In the event that multiple cohorts are open in Parts B and/or C simultaneously, participants will be assigned to those cohorts in an alternating fashion.

During dose escalation (Preliminary Safety Cohorts and Part A), participants who are not evaluable for DLT determination may be replaced (see Section 5.1.2.1). Replacement participants will be assigned to the same part (Part A) and dose, but will be assigned a new participant number. Please refer to the IRT manual for complete details on replacement of participants.

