7.3.2 BMS-986226 Dose-limiting Toxicities

For the purpose of guiding dose escalation, DLTs will be defined based on the incidence, intensity, and duration of AEs for which no clear alternative cause is identified. The DLT period will be 35 days (5 weeks).

In the Preliminary Safety Cohorts, participants who have received 1 dose of BMS-986226 and have completed, or who discontinued due to a DLT in the 4-week DLT period, will be considered as DLT-evaluable participants for BMS-986226 monotherapy.

In Part A, participants who have received 2 doses of BMS-986226 and have completed, or who discontinued due to a DLT in the 5-week DLT period, will be considered as DLT-evaluable participants for BMS-986226 monotherapy.

In Parts B, C, D and E, participants receiving either 1 dose of BMS-986226 or 2 doses of either nivolumab or ipilimumab, or participants who discontinued due to a DLT in the 5-week combination treatment DLT period, will be considered as DLT-evaluable participants for combination treatment. Participants who withdraw from the study during the DLT evaluation period or have received less than 2 doses for reasons other than a DLT in the monotherapy (Part A) or 1 dose in combination therapy (Parts B, C, D, E), will not be considered as DLT-evaluable participants in Part A, who are dose delayed during the DLT evaluation period for reasons other than a DLT could be considered as DLT-evaluable participants if they receive at least 2 doses of therapy.

For the purpose of participant management, any AE that meets DLT criteria, regardless of the cycle in which it occurs, will lead to discontinuation of study treatment (except as defined in Section 7.3.5). Participants who withdraw from the study during the 5-week DLT evaluation period for reasons other than a DLT may be replaced with a new participant at the same dose

level. The incidence of DLT(s) during the 5-week DLT evaluation period will be used in dose escalation decisions through application of the BLRM/BLRM-Copula model. AEs occurring after the DLT period will be considered to enhance the robustness of BLRM/BLRM-Copula prediction, upon agreement between the Sponsor, Medical Monitor/Study Director (or designee), and investigators.

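### The DLT rate by dose level is set on all treated participants, not DLT-evaluable ones, which normally understates the reported in-window rate at dose levels that have both a DLT and a non-evaluable participant

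*Combined protocol and SAP*

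**What the plan says.** Incidence of "AEs meeting protocol defined DLT criteria" is part of the primary endpoint (Synopsis; Table 4-1).

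Section 10.3.2 gives one rule for the analysis set: "All safety analyses for will be performed on the treated population" (wording as printed). The methods listed under it begin "DLT rate by dose level; frequency distribution of treated participants with AE using the worst CTC grade", and no other denominator is named for the first of these. Section 10.2 defines treated as "All participants who received any dose of study treatment". It repeats the rule in a sentence that covers safety and ends "immunogenicity will be based on all treated participants". Its populations are enrolled, treated, response-evaluable, pharmacokinetic and immunogenicity; none is DLT-evaluable.

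Section 7.3.2 does define DLT evaluability. For monotherapy escalation it reads "In Part A, participants who have received 2 doses of BMS-986226 and have completed, or who discontinued due to a DLT", with a 5-week period. Those who withdraw in the window, or receive too few doses, for reasons other than a DLT "will not be considered as DLT-evaluable participants". Section 7.1.1 adds, for monotherapy escalation, that "participants who are not evaluable for DLT determination may be replaced". Sections 5.1.2.1, 5.1.2.3 and 7.3.2 likewise let a participant who withdraws in the window for a non-DLT reason be replaced at the same dose level.

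The design itself counts DLT-evaluable participants: at most 12 per dose level (Section 10.1.1; Appendix 10, Section 2) and a stop at 30 (Appendix 10, Section 2).

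**The concern.** A DLT rate is a proportion of people observed long enough, at sufficient dose, to have shown a DLT. The protocol recognises this in Section 7.3.2 and then does not carry it into the analysis section. A participant who leaves the window early for progression or withdrawal has not been fully observed, yet under Section 10.3.2 counts as a full denominator unit with no DLT. Because such participants may be replaced, a dose level can hold more treated than evaluable participants.

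At stake is a component of the primary safety summary. Readers will compare the tabulated rate with the 16% to 33% target range. Wherever a participant was non-evaluable, the rate will not match the data used for the MTD recommendation. Dose levels with different numbers of non-evaluable participants will also not be comparable with each other.

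**Working it through.** **1. The plan's own figures.** Sections 10.1.2 and 10.1.3 give the probability of seeing at least one event, in evaluable participants, as 1 − (1 − p)^n:

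- n = 6, p = 0.24: 1 − 0.76^6 = 0.807 (stated: about 80%)
- n = 12, p = 0.24: 1 − 0.76^12 = 0.963 (stated: up to 96%)
- n = 40, p = 0.05: 1 − 0.95^40 = 0.871 (stated: about 87%)

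All three reproduce. Planning is therefore in evaluable participants, while the reported rate is in treated participants.

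**2. The dilution.** Let x be the participants with a DLT in the DLT period, n the DLT-evaluable participants at that dose level, and k the treated but non-evaluable participants. Someone who stops for a DLT in the window is evaluable by definition, so the k participants normally contribute nothing to x.

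- Rate on the evaluable set: x/n
- Rate on the treated set: x/(n + k)
- Ratio of the two: n/(n + k)

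**3. Numbers.** The documents give no non-evaluable rate, so k = 1 to 3 is an assumed range. Six is the planned size per dose level in Parts B1 and C1 and the minimum for declaring an MTD; twelve is the cap.

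| x/n | evaluable | k = 1 | k = 2 | k = 3 |
|---|---|---|---|---|
| 1/6 | 16.7% | 14.3% | 12.5% | 11.1% |
| 2/6 | 33.3% | 28.6% | 25.0% | 22.2% |
| 4/12 | 33.3% | 30.8% | 28.6% | 26.7% |
| multiplier, n = 6 | 1 | 0.86 | 0.75 | 0.67 |
| multiplier, n = 12 | 1 | 0.92 | 0.86 | 0.80 |

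At n = 6, k = 3 means that 3 of 9 treated participants (33%) are non-evaluable, so it is the extreme of the range; k = 1 and k = 2 correspond to 1/7 = 14% and 2/8 = 25%.

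**4. Where it applies.**

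- With x = 0 the rate is 0% on either set; only its apparent precision is overstated.
- The effect is probably largest in Part A, where evaluability needs 2 doses. In Parts B to E, 1 dose of BMS-986226 can suffice, so mainly withdrawals within the window dilute the rate.
- Replacement for missing paired biopsies (Section 7.1.1) does not itself dilute, since such a participant can still be DLT-evaluable.

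**The case against.** **Treated is the usual safety set.** It is, and it should stay for AEs, SAEs and laboratory data. Only the window-based DLT rate needs a different one.

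**The protocol uses a treated denominator elsewhere.** The 33% rule for interrupting enrolment in Parts D and E (Section 5.1.2.4) is stated across all participants treated. That is a separate monitoring rule with its own stated denominator. It gives no reason to use that denominator for the rate by dose level, and nothing here requires it to change.

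**The numerator has no time window.** This stands. Section 10.3.2 does not confine DLT-criteria events to the DLT period. A Part A participant who stops after one dose for another reason could have a qualifying event during the 100-day follow-up and so enter the treated numerator. A reader might infer that non-evaluable participants can never add to the numerator, so that the rate is always too low. The documents support that direction, normally, only for in-window DLTs. This is a reason to define numerator and denominator together.

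**The SAP is still to come.** Section 10.3 says it will be finalised before database lock, so there is room to correct this. But the protocol text says all safety analyses, and an SAP that follows it would reproduce the problem.

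**No dose decision changes.** This also stands. A reader might infer from 2/6 becoming 2/8 that a dose moves from the excessive-toxicity category into the target range. The documents do not support that: Appendix 10 (Sections 2 and 5) applies the 16% and 33% limits to the posterior probability of the true DLT rate, not to an observed proportion, and the models use DLT-period data.

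**Conclusion.** Wrong as written, moderate severity. Followed exactly, Section 10.3.2 puts an in-window DLT rate on a denominator that includes people whom Section 7.3.2 says cannot be assessed for it. At dose levels with at least one DLT, the reported rate is normally multiplied by n/(n + k). With 6 evaluable participants and one or two non-evaluable, that is a relative understatement of 14% or 25% (1/7 or 2/8).

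The size rests on the assumed k and on non-evaluable participants having no in-window DLT. The harm is confined to the reported primary safety estimate and its agreement with the BLRM data. Escalation, overdose control and MTD selection are not affected. The endpoint is descriptive, with no formal hypothesis tested, which is a further reason not to rate the point higher.

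**What to change.** - **Section 10.2:** add a DLT-evaluable population, using the Section 7.3.2 definition for each study part.
- **Section 10.3.2 and the SAP:** define the DLT rate by dose level as participants with a DLT within the DLT period (4 weeks in the Preliminary Safety Cohorts, 5 weeks elsewhere) divided by DLT-evaluable participants. Report beside it the number treated but not evaluable at each dose level.
- **Keep on the treated population:** the incidence of AEs meeting DLT criteria at any time, as a separate line, together with the other AE, SAE and laboratory summaries.
- **Leave unchanged:** the 33% rule for Parts D and E.

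The cost is a few lines of text and one extra column in a table. The evaluability definition already exists and is needed to apply the escalation caps, so data collection and trial conduct do not change.
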